4.2.3 Exposure and compliance

Exposure and treatment compliance derivation details are defined in Section 3.3.1.

Extent of exposure to IP, compliance, and total number of dosing occasions will be summarised by treatment group, for the safety analysis set.

The date and time of IP administrations, and all missed doses will be listed using the safety analysis set.

4.2.4 Primary outcome variables

4.2.4.1 Primary analyses

The primary variables of within subject change from baseline to EOT, expressed as ratio i.e. (EOT/baseline) in numbers of each of the airway submucosal inflammatory cells will be analysed using evaluable analysis set and FAS separately for eosinophils, neutrophils, T cells (CD3+, and CD4+), mast cells tryptase+, and mast cells chymase+ using an analysis of covariance (ANCOVA) including baseline value, treatment, and stratification factor (screening blood eosinophils count: < 150 cells/ μ L, 150 - < 300 cells/ μ L, \geq 300 cells/ μ L at Visit 1) as covariates. The analyses will be performed by using log-transformed data and estimated geometric means and the ratio of geometric means with both 2-sided 90% and 95% confidence intervals (CIs), and p-values will be presented. The results will also be summarised graphically using a forest plot.

If the change from baseline for a subject, expressed as a ratio, is zero, the value will be replaced by half the smallest observed value among the subjects with non-zero values, before doing the logarithmic transformation. If the baseline value for a subject is zero, the baseline value will be replaced by half the smallest observed value among subjects with non-zero values, before calculating the change from baseline. If both baseline and a post-baseline value for a subject is zero, the corresponding value for the ratio is defined to be 1.

Available values at both baseline and EOT are required for a subject to be included in the analysis and it is unlikely that a subject with a missing baseline value will undergo a second biopsy.

All hypothesis testing will be reported using 2-sided tests with a nominal 10% significance level and 90% CIs. For publishing purposes, 95% CIs will also be reported. The direction of interest for each of the primary endpoints is that the ratio tezepelumab/placebo is lower than 1.

The supportive variables of within subject absolute change from baseline to EOT in numbers of each of the airway submucosal inflammatory cells will be analysed using evaluable analysis set separately for eosinophils, neutrophils, T cells (CD3+, and CD4+), mast cells tryptase+, and mast cells chymase+, using the same ANCOVA model described for the primary variables. The analyses will be performed and estimated means and difference estimates with 2-sided 90% and 95% confidence intervals, and p-values will be presented. The results will also be summarised graphically using a forest plot.

Summary statistics including number of subjects, mean, standard deviation (SD), median, minimum, maximum, geometric mean, and coefficient of variation of geometric mean for absolute values at each visit in number of airway submucosal inflammatory cells will be presented separately for eosinophils, neutrophils, T cells (CD3+, and CD4+), mast cells tryptase+, and mast cells chymase+, based on the evaluable analysis set by randomised treatment group. For change from baseline to EOT, expressed as a ratio, summary statistics including number of subjects, median, minimum, maximum, geometric mean, coefficient of variation of geometric mean, and SD of log values will be presented. Coefficient of variation of geometric mean is calculated as $\sqrt{(\exp(\text{std}^2)-1)*100\%}$, where std is the standard deviation of the log-transformed values. For absolute change from baseline to EOT, summary statistics including number of subjects, mean, SD, median, minimum, and maximum will be presented based on evaluable analysis set.

For time point summary statistics using log-transformed values in efficacy variables, if a baseline or post-baseline value for a subject is zero, the value will be replaced by half the smallest observed value among subjects with non zero values, before calculating the log-transformed value.

4.2.4.2 Multiplicity adjustment of primary outcome variables

Nominal p-values will be calculated for airway submucosal inflammatory cells separately for eosinophils, neutrophils, T cells (CD3+, and CD4+), mast cells tryptase+, and mast cells chymase+ . No multiplicity adjustment of primary outcome variables will be performed.

4.2.4.3 Subgroup analysis of primary outcome variables

Efficacy for the primary variables will be evaluated within each subgroup using the evaluable analysis set.

The subgroup analysis of the primary variables by stratification factor (screening blood eosinophils count: < 150 cells/ μ L, $150 - < 300$ cells/ μ L, ≥ 300 cells/ μ L) will use the same ANCOVA model described for the primary variable in Section 4.2.4.1, and also include the stratification factor by treatment interaction. The subgroup analysis of primary variables by other subgroup factors, ie, gender, race, age, baseline FeNO group, baseline perennial specific IgE status (FEIA): allergic and non-allergic, baseline total serum IgE group, baseline IL-5 group, and baseline IL-13 group, will be analysed separately using the same ANCOVA model as in Section 4.2.4.1 with the addition of elements in the ANCOVA model for subgroup factor, and interactions between subgroup and treatment. The analysis of primary variables by baseline blood eosinophils subgroups will not include stratification factor as an element in the ANCOVA model. The analyses will be performed using log-transformed data. The estimated geometric means and the ratio of geometric means with 2-sided 90% and 95% CIs and p-values will be presented for each subgroup. Results will be summarised graphically using a forest plot.

Descriptive summaries of the primary variables will be presented for the specified categorical variables above, irrespective of how few subjects there are in any particular subgroups.

For model-based analyses, if any of the subgroups have fewer than 10 subjects in one or both treatment groups, this subgroup level will not be included in the model. If that leaves only one subgroup level, the model will not be fitted for that categorical variable. If it leaves more than one subgroup level, the model will be fitted using the remaining subgroups which have 10 or more subjects in both treatment groups.

The same summary statistics provided for the primary variables will be presented for each of the primary variables within all subgroups based on the evaluable analysis set by randomised treatment group.

4.2.5 Secondary outcome variables

The secondary variables of within subject change, expressed as a ratio, from baseline to EOT in RBM thickness and % airway epithelial integrity, will be analysed using evaluable analysis set and the same ANCOVA model described for the primary variable, which includes baseline value, treatment, and stratification factor as covariates. The analysis will also be performed by using log-transformed data and estimated geometric means and the ratio of geometric means

with 2-sided 90% and 95% confidence intervals, and p-values will be presented. The results will also be summarised graphically using a forest plot.

The secondary variables of within subject change, expressed as a ratio, from baseline to week 28 in numbers of each of the airway submucosal inflammatory cells for eosinophils, neutrophils, T cells (CD3+, and CD4+), mast cells tryptase+, and mast cells chymase+ across the spectrum of T2 status, will be analyzed separately using the same ANCOVA model described for the primary variables with the addition of elements in the ANCOVA model for T2 quartile (categorical) and interactions between T2 quartile and treatment. The analyses will be performed by using log-transformed data. The ratio of geometric mean and the ratio of geometric means with 2-sided 90% and 95% CIs, and p-values will be presented.

The supportive variables of within subject absolute change from baseline to week 28 in RBM thickness, % airway epithelial integrity, and numbers of each of the airway submucosal inflammatory cells for eosinophils, neutrophils, T cells (CD3+, and CD4+), mast cells tryptase+, and mast cells chymase+ across the spectrum of T2 status will be analysed separately using the same ANCOVA model described for the primary variables. The analyses will be performed and estimated means and difference estimates with 2-sided 90% and 95% confidence intervals, and p-values will be presented. The results will also be summarised graphically using a forest plot.

The subgroup analysis of RBM thickness by baseline blood eosinophils (< 150 cells/ μ L, 150 - < 300 cells/ μ L, \geq 300 cells/ μ L), baseline FeNO group, and baseline perennial specific IgE status based on evaluable analysis set will be performed in the same manner as the subgroup analyses of primary variables.

The same summary statistics provided for the primary variables will be presented for each of the secondary and supportive variables and subgroup analyses of RBM thickness based on the evaluable analysis set by randomised treatment group.

To explore the relationship of change from baseline in primary variables and T2 status, the LOESS scatterplots will be generated for log-ratios i.e. (EOT/baseline) in inflammatory cell counts versus T2 status (continuous) by treatment group for each inflammatory cell type for evaluable analysis set. The box plots for log-ratios i.e. (EOT/baseline) in inflammatory cell counts will also be generated by treatment within each T2 quartile (categorical). The results of the T2 status analyses will be reported separately from the CSR in a scientific report or publication.

4.2.6 Sensitivity analyses for primary and secondary outcome variables

Any sensitivity analyses will be determined and documented prior to database lock of the study. The COVID-19 related sensitivity analyses for primary and secondary outcome variables are described in Appendix 8.3.

4.2.7 Exploratory objectives

CCI

CCI

[Redacted]

[Redacted]

[Redacted]

[Redacted]

[Redacted]

[Redacted]

[Redacted]

[Redacted]

[Redacted]

[Redacted]

[Redacted]

4.2.8 Safety and tolerability

All safety variables will be summarised using the safety analysis set (see Section 2.1.2 for details).

4.2.8.1 AEs

AEs will be summarised separately for the on-treatment and on-study periods, as defined in Section 3.3.3 unless stated otherwise. All AE summaries will be presented by actual treatment group. AEs occurring during the screening/run-in period, or occurring post-treatment will be listed, but not summarised separately.

An overall summary table will be produced showing the number and percentage of subjects with at least one AE in each of the following categories: any AEs, SAEs, AEs with a fatal outcome, AEs leading to discontinuation of IP (DAEs), and AESIs. The total number of AEs in the different AE categories will also be presented as well as the number of subjects (i.e. accounting for multiple occurrences of the same event in a subject).

All AEs will be summarised by SOC and PT assigned to the event using the MedDRA dictionary by descending frequency order in the tezepelumab treatment group. For each PT, the

number and percentage of subjects reporting at least one occurrence of the event will be presented (i.e. subjects with multiple occurrences of the same PT will only be counted once).

Similar summaries by SOC and PT will also be presented for:

- SAEs
- Fatal AEs
- DAEs
- DAEs causally related to IP
- SAEs leading to discontinuation of IP
- Each AESI category separately
- The most common AEs (defined as those occurring in >3% of subjects in either treatment group) – by PT only

All AEs (by PT) will be summarised additionally by causality and maximum intensity. If a subject reports multiple occurrences within each PT, the maximum intensity will be taken as the highest recorded (the order being mild, moderate and severe) respectively.

Exposure-adjusted summaries by SOC and PT will also be presented for all AEs.

The COVID-19 related safety analyses are described in Appendix 8.3.

4.2.8.2 Laboratory data

All laboratory data will be presented in SI units. All continuous laboratory variables will be summarised by absolute value at each visit by treatment group, together with the corresponding changes from baseline. These summaries will be produced for the on-study period, as defined in Section 3.1.5. The summary statistics presented will be the minimum, 1st quartile, median, 3rd quartile, maximum, mean and SD.

Central laboratory normal reference ranges will be used for the identification of individual clinically important abnormalities. A shift table will be produced for each laboratory variable to display low, normal, and high values. The shift tables will present baseline and maximum/minimum/last post-baseline values for each variable.

Shift plots showing each individual subject's laboratory value at baseline and at maximum/minimum/last value post-baseline will be produced for each continuous laboratory variable. If any laboratory variables show any unusual features (high or low values or a general shift in the data points) at other time points then shift plots of these data may be produced. The diagonal line of no change will also be displayed on the shift plots.

Both shift tables and shift plots will be produced using all data for the on-study period, as defined in Section 3.1.5.

The frequencies of clinically noteworthy values (using normal reference ranges) occurring during the study will also be given.

In order to identify potential Hy's Law cases, maximum post-baseline TBL will be plotted separately against both maximum post-baseline ALT and AST, expressed as multiples of ULN. These plots will be produced on a log scale, with reference lines included at 2xULN for TBL, and at 3xULN for both ALT and AST. These plots will be produced using all data for the on-study period.

For all subjects who meet the biochemical criteria for Hy's Law (potential Hy's Law cases), the relevant laboratory variables may be tabulated showing all visits for these subjects.

Subjects with elevated ALT or AST in addition to elevated TBL at any time may be explored further graphically using individual subject profile plots.

For urinalysis data, a shift table will be generated for each variable to display negative (0), positive (trace or +) or strongly positive (++, +++, or >+++). The shift tables will present changes from baseline to maximum/last value post-baseline for each variable. All data for the on-study period will be used.

4.2.8.3 Vital signs

All vital signs variables will be summarised by absolute value at each visit by treatment group, together with the corresponding changes from baseline. This will also include weight and BMI. These summaries will be produced for the on-study period, as defined in Section 3.1.5. The summary statistics presented will be the minimum, 1st quartile, median, 3rd quartile, maximum, mean and SD.

AZ-defined reference ranges (see Section 3.3.5) will be used for the identification of individual abnormalities. A shift table will be produced for each vital signs variable to display low, normal, and high values. The shift tables will present baseline and maximum/minimum/last post-baseline values for each variable.

Shift plots showing each individual subject's vital signs value at baseline and at maximum/minimum/last value post-baseline will be produced for each continuous vital signs variable.

Both shift tables and shift plots will be produced using all data for the on-study period, as defined in Section 3.1.5.

Subjects who have treatment-emergent changes from baseline outside the pre-defined AZ clinically important change criteria in Section 3.3.5 will be summarised. All data for the on-study period will be used.

4.2.8.4 12-lead or 15-lead ECG

A shift table will be produced for each ECG parameter to display normal (includes borderline), abnormal - not clinically significant, abnormal - clinically significant, and not done. The shift tables will present baseline and last observation post-baseline value for the on-study period, as defined in Section 3.1.5.

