3. PRIMARY AND SECONDARY VARIABLES

3.1 General definitions

3.1.1 Definition of baseline

In general, the last non-missing measurement on or prior to the date of randomisation will serve as the baseline measurement for efficacy variables. If there is no value on or prior to the date of randomisation, then the baseline value will not be imputed, and will be set to missing.

In general, the last non-missing measurement prior to the first dose of study treatment will serve as the baseline measurement for safety, pharmacokinetic and immunogenicity variables. If there is no value prior to first dose of study treatment, then the baseline value will not be imputed, and will be set to missing.

Where unscheduled/repeat assessments are relevant and exist for any subject at a particular visit specified below, they will also be considered in the baseline definitions, provided they remain on or prior to the date of randomisation (efficacy) or prior to the date of first dose of study treatment (safety).

For daily assessments which are made in both morning and evening, the whole day is defined by the assessments in the evening and the following morning. The daily assessment will be considered missing if either evening or following morning is missing. However, some analyses may consider morning and evening separately.

For safety variables (vital signs, weight/body mass index (BMI), haematology, clinical chemistry, urinalysis, 12- or 15-lead ECG), baseline will be defined as the latest non-missing assessment prior to first dose. If no time is recorded for an assessment, and the assessment takes place at Visit 3b, this will be assumed to be a pre-dose assessment.

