3.1.5 Study periods

The following study periods are defined for analysis purposes:

- Screening/run-in period: starting on the date of the first study procedure and ending one day prior to randomisation (for randomised subjects) or on the date of the last study procedure (for screening failures). If any subject is re-screened, the latest available screening will be used for this purpose.
- Planned treatment period: starting on the date of randomisation (efficacy) / date of first dose of IP (safety) and ending on the date of the EOT visit or earlier study withdrawal date (for subjects not followed up until the EOT visit)
- On-treatment period: starting on the date of randomisation (efficacy) / date of first dose of IP (safety) and ending on minimum (date of last dose of IP + 35 days, date of death, date of study withdrawal).
- Post-treatment period/Follow-up period: starting one day after the end date of on-treatment period and ending on the study completion or withdrawal date.
- On-study (on-treatment and post-treatment) period: starting on the date of randomisation (efficacy) / date of first dose of IP (safety) and ending on the study completion or withdrawal date.

Efficacy analyses will use data collected during the planned treatment period, except for lung function and some biomarker data that will use data collected at the protocol specified time points for the on-study period.

Safety analyses will be presented for data collected during the on-treatment period and on-study period.

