3.3.6 Electrocardiogram

Either 12-lead or 15-lead ECG measurements will be recorded in accordance with the protocol, with the baseline visit being defined as V1.

The outcome of the overall evaluation (normal, abnormal or borderline) will be taken directly from the eCRF, as will the assignment of clinically significance.

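### The only ECG summary is a shift to the last on-study recording, so resolved abnormalities are missing from it; separately, the SAP defines the ECG baseline in two ways

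*SAP*

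**What the plan says.** ECGs are a named safety outcome in SAP section 1.1.3. Section 4.2.8.4 specifies a single type of output: "A shift table will be produced for each ECG parameter to display normal (includes borderline), abnormal - not clinically significant, abnormal - clinically significant", with a further category for not done. On timing it says "The shift tables will present baseline and last observation post-baseline value for the on-study period". It gives no worst-value, by-visit or on-treatment ECG summary.

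Section 3.1.5 defines the period as "On-study (on-treatment and post-treatment) period", so it runs past the end of treatment into follow-up. The same section says in general terms: "Safety analyses will be presented for data collected during the on-treatment period and on-study period". Section 3.1.6 includes unscheduled and repeat data in baseline definitions and in any maximum, minimum or last value within the period.

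For laboratory data, section 4.2.8.2 says "The shift tables will present baseline and maximum/minimum/last post-baseline values for each variable". Section 4.2.8.3 says the same for vital signs. Urinalysis, which is categorical, is shown at maximum and last (section 4.2.8.2).

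On the starting point, section 3.1.1 lists ECG among the safety variables for which "baseline will be defined as the latest non-missing assessment prior to first dose". Section 3.3.6 instead describes the ECG recordings "with the baseline visit being defined as V1".

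**The concern.** There are two defects, and they are independent.

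The first concerns the end of the shift. A table that ends on the last recording cannot show an abnormality that appeared and then resolved. That includes one that resolved after dosing stopped, which is a pattern a safety reader wants to see. The SAP avoids this for laboratory values, vital signs and urinalysis by also showing an extreme value. It gives no reason for treating ECG differently.

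The second concerns the start of the shift. With two baseline rules in the current text, two programmers could place the same subject in different rows of the table, each with a section of the SAP to cite.

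**Working it through.** The SAP states no figure to reproduce. The check sets the rules side by side, applies them to simple cases, and works out the timing.

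**End of the shift.**

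| Safety variable | Post-baseline value in shift table | Section |
|---|---|---|
| Laboratory | maximum, minimum, last | 4.2.8.2 |
| Urinalysis | maximum, last | 4.2.8.2 |
| Vital signs | maximum, minimum, last | 4.2.8.3 |
| ECG | last only | 4.2.8.4 |

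Three hypothetical subjects, all normal at baseline:

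| Post-baseline ECGs | Shift to last | Shift to worst |
|---|---|---|
| Clinically significant abnormality on treatment, later ECG normal | normal to normal | normal to abnormal, clinically significant |
| One scheduled ECG abnormal, unscheduled repeat normal | normal to normal | normal to abnormal |
| One post-baseline ECG only, abnormal | normal to abnormal | same |

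The second row follows from section 3.1.6: the repeat is the later value and displaces the abnormal one. The loss can therefore occur even if the protocol schedules only one post-baseline ECG.

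**Can the last recording be off treatment?** The inputs are Table 1 and its footnote (EOT on target day 197, 4 weeks after last dose; Week 40 follow-up on day 281) and section 3.1.5 (on-treatment period ends at last dose + 35 days).

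- Last dose: 197 − 28 = day 169.
- End of on-treatment period: 169 + 35 = day 204.
- Week 40 follow-up: 281 − 169 = 112 days after last dose, and 281 − 204 = 77 days after the on-treatment period ends.

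If an ECG is taken at the final follow-up (an assumption), the tabulated value is an off-treatment one. If the last ECG is at EOT, day 197 falls inside the on-treatment period, and only earlier or repeated on-treatment recordings can be masked.

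**Size.** If a share r of post-baseline abnormalities has resolved by the last recording, the table misses exactly that share. The SAP gives neither r nor the ECG schedule, so r can lie anywhere from 0 to 1.

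**Start of the shift.** Section 3.1.1 says "12- or 15-lead ECG), baseline will be defined as the latest non-missing assessment prior to first dose". It admits repeats and treats an untimed Visit 3b assessment as pre-dose. Section 3.3.6 fixes Visit 1.

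| Pre-dose ECGs | Baseline under 3.1.1 | Baseline under 3.3.6 |
|---|---|---|
| Visit 1 only | Visit 1 | Visit 1 |
| Visit 1 abnormal, clinically significant; later pre-dose ECG normal | normal | abnormal, clinically significant |

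Suppose the second subject's last post-baseline ECG is abnormal and clinically significant. The table then shows a normal-to-abnormal shift under 3.1.1 and no shift under 3.3.6.

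**The case against.** - **Adverse events.** An ECG abnormality reported as an adverse event still appears in the adverse event tables, which cover both the on-treatment and on-study periods (section 4.2.8.1), and the DSMB reviews safety data regularly (section 5). This stands. A reader might infer that a resolved abnormality vanishes from the safety output altogether, and the SAP does not support that. It does support something narrower: the SAP states the route to adverse event reporting for physical examination findings (sections 3.3.7 and 4.2.8.5) but not for ECG. The protocol may do so. An abnormality not reported as an adverse event appears in no summary the SAP specifies.
- **Period.** A reader might infer that ECG alone is denied an on-treatment presentation. It is not: the laboratory and vital signs summaries and shift tables are also on-study only, and the amendment history records that choice for all three together. The ECG-specific difference is last versus extreme value. The general statement in section 3.1.5 still favours an on-treatment version, but this is a weaker argument.
- **Linking the two defects.** It would be wrong to say that the double baseline makes resolved abnormalities disappear. It changes the starting category only.
- **Schedule.** With one post-baseline ECG per subject, last equals worst. With Visit 1 as the only pre-dose ECG, the two baselines coincide. Both stand, and they limit the size. They do not remove the contradiction in the text or the effect of repeats.
- **A reconciling reading.** Section 3.3.6 may only name the visit at which the baseline ECG is scheduled, with 3.1.1 as the derivation rule. That is plausible, but the text does not say so.

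**Conclusion.** Both points hold, separately. The only specified ECG summary omits any abnormality that has normalised by the last on-study recording, and this departs from the SAP's own practice for laboratory, vital signs and urinalysis shift tables. The ECG baseline is defined in two ways that disagree for any subject with an ECG after Visit 1 and before first dose.

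The size of either effect cannot be stated from the SAP. The first needs more than one post-baseline ECG in a subject, repeats included; the second needs more than one pre-dose ECG. No primary or secondary efficacy result depends on this table. The table is a presentation choice that can be improved cheaply. The baseline conflict is an error in the text and should be corrected whatever the schedule.

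**What to change.** 1. In section 4.2.8.4, add a shift from baseline to the worst post-baseline category, ordered as normal or borderline; abnormal, not clinically significant; abnormal, clinically significant. Keep the shift to last observation. An on-treatment version of the worst-category table would also follow the general statement in section 3.1.5.
2. In section 3.3.6, replace Visit 1 with the section 3.1.1 rule (latest non-missing ECG before first dose), so that one baseline applies throughout.
3. While editing, clarify the unit of the table: section 4.2.8.4 refers to each ECG parameter, whereas section 3.3.6 describes only an overall evaluation and its clinical significance.

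The cost is one extra table from data already collected (two if the on-treatment version is added) and a short wording change. The worst-category table will show somewhat more abnormalities in both arms, since a worst value picks up transient and incidental findings. It adds nothing for a subject with a single post-baseline ECG.
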